### **5.2.3 Trial Blinding/Masking**

This is an open-label trial; therefore, the Sponsor, investigator and subject will know the treatment administered.

Although this is an open-label trial, the study team at the Sponsor consisting of the clinical, statistics and data management personnel will remain blinded to PD-L1 patient-level biomarker results until the time that a study report is written. While the study team is blinded to PD-L1 patient-level biomarker results, access to the PD-L1 patient-level biomarker results will be limited to an unblinded Sponsor statistician and Sponsor statistical programmer who will be responsible for data review but who have no other responsibilities associated with the trial.

### **5.3 Randomization or Treatment Allocation**

Allocation will occur centrally using an interactive voice response system / integrated web response system (IVRS/IWRS). There is one treatment arm. Subjects will be assigned pembrolizumab (MK-3475).

### **5.4 Stratification**

No stratification based on age, sex or other characteristics will be used in this trial.

### **5.5 Concomitant Medications/Vaccinations (Allowed & Prohibited)**

Medications or vaccinations specifically prohibited in the exclusion criteria are not allowed during the ongoing trial. If there is a clinical indication for any medication or vaccination specifically prohibited during the trial, discontinuation from trial therapy or vaccination may be required. The investigator should discuss any questions regarding this with the Sponsor Clinical Director. The final decision on any supportive therapy or vaccination rests with the investigator and/or the subject's primary physician. However, the decision to continue the subject on trial therapy or vaccination schedule requires the mutual agreement of the investigator, the Sponsor and the subject.

#### **5.5.1 Acceptable Concomitant Medications**

All treatments that the investigator considers necessary for a subject's welfare may be administered at the discretion of the investigator in keeping with the community standards of medical care. All concomitant medication will be recorded on the case report form (CRF) including all prescription, over-the-counter (OTC), herbal supplements, and IV medications and fluids. If changes occur during the trial period, documentation of drug dosage, frequency, route, and date may also be included on the CRF.

All concomitant medications received within 30 days before the screening visit and 30 days after the last dose of trial treatment should be recorded. Concomitant medications administered after 30 days after the last dose of trial treatment should be recorded for SAEs and ECIs as defined in Section 7.2.

### 5.5.2 Prohibited Concomitant Medications

Subjects are prohibited from receiving the following therapies during the Screening and Treatment Phase (including retreatment for post-complete response relapse) of this trial:

- Antineoplastic systemic chemotherapy or biological therapy
- Immunotherapy not specified in this protocol
- Chemotherapy
- Investigational agents other than pembrolizumab (MK-3475)
- Radiation therapy
  - Note: Radiation therapy to a symptomatic solitary lesion or to the brain may be allowed after consultation with Sponsor.
- Live vaccines within 30 days prior to the first dose of trial treatment and while participating in the trial. Examples of live vaccines include, but are not limited to, the following: measles, mumps, rubella, varicella/zoster, yellow fever, intranasal influenza, rabies, BCG, and typhoid vaccine.
- Glucocorticoids for any purpose other than to modulate symptoms from an event of clinical interest of suspected immunologic etiology. The use of physiologic doses of corticosteroids may be approved after consultation with the Sponsor.

*Note: Use of prophylactic corticosteroids to avoid allergic reactions (e.g. IV contrast dye) is permitted.*

Subjects who, in the assessment by the investigator, require the use of any of the aforementioned treatments for clinical management should be discontinued from study medication. Subjects may receive other medications that the investigator deems to be medically necessary.

The Exclusion Criteria describes other medications which are prohibited in this trial.

There are no prohibited therapies during the Post-Treatment Follow-up Phase.

### 5.6 Rescue Medications & Supportive Care

Subjects should receive appropriate supportive care measures as deemed necessary by the treating investigator. Suggested supportive care measures for the management of adverse events with potential immunologic etiology are outlined below and in greater detail in the ECI guidance document. Where appropriate, these guidelines include the use of oral or intravenous treatment with corticosteroids as well as additional anti-inflammatory agents if symptoms do not improve with administration of corticosteroids. Note that several courses of steroid tapering may be necessary as symptoms may worsen when the steroid dose is decreased. For each disorder, attempts should be made to rule out other causes such as metastatic disease or bacterial or viral infection, which might require additional supportive care. The treatment guidelines are intended to be applied when the investigator determines the events to be related to pembrolizumab.

Note: if after the evaluation the event is determined not to be related, the investigator is instructed to follow the ECI reporting guidance but does not need to follow the treatment guidance (as outlined in the ECI guidance document). Refer to Section 5.2.1 for dose modification.

It may be necessary to perform conditional procedures such as bronchoscopy, endoscopy, or skin photography as part of evaluation of the event. Suggested conditional procedures, as appropriate, can be found in the ECI guidance document.

- **Pneumonitis:**

- For **Grade 2 events**, treat with systemic corticosteroids. When symptoms improve to Grade 1 or less, steroid taper should be started and continued over no less than 4 weeks.
- For **Grade 3-4 events**, immediately treat with intravenous steroids. Administer additional anti-inflammatory measures, as needed.
- Add prophylactic antibiotics for opportunistic infections in the case of prolonged steroid administration.

- **Diarrhea/Colitis:**

Subjects should be carefully monitored for signs and symptoms of enterocolitis (such as diarrhea, abdominal pain, blood or mucus in stool, with or without fever) and of bowel perforation (such as peritoneal signs and ileus).

- All subjects who experience diarrhea/colitis should be advised to drink liberal quantities of clear fluids. If sufficient oral fluid intake is not feasible, fluid and electrolytes should be substituted via IV infusion. For Grade 2 or higher diarrhea, consider GI consultation and endoscopy to confirm or rule out colitis.
- For **Grade 2 diarrhea/colitis** that persists greater than 3 days, administer oral corticosteroids.
- For **Grade 3 or 4 diarrhea/colitis** that persists > 1 week, treat with intravenous steroids followed by high dose oral steroids.
- When symptoms improve to Grade 1 or less, steroid taper should be started and continued over no less than 4 weeks.

- **Type 1 diabetes mellitus (if new onset, including diabetic ketoacidosis [DKA]) or  $\geq$  Grade 3 Hyperglycemia, if associated with ketosis (ketonuria) or metabolic acidosis (DKA)**

- For **T1DM or Grade 3-4 Hyperglycemia**
  - Insulin replacement therapy is recommended for Type I diabetes mellitus and for Grade 3-4 hyperglycemia associated with metabolic acidosis or ketonuria.
  - Evaluate patients with serum glucose and a metabolic panel, urine ketones, glycosylated hemoglobin, and C-peptide.

• **Hypophysitis:**

- For **Grade 2** events, treat with corticosteroids. When symptoms improve to Grade 1 or less, steroid taper should be started and continued over no less than 4 weeks. Replacement of appropriate hormones may be required as the steroid dose is tapered.
- For **Grade 3-4** events, treat with an initial dose of IV corticosteroids followed by oral corticosteroids. When symptoms improve to Grade 1 or less, steroid taper should be started and continued over no less than 4 weeks. Replacement of appropriate hormones may be required as the steroid dose is tapered.

• **Hyperthyroidism or Hypothyroidism:**

Thyroid disorders can occur at any time during treatment. Monitor patients for changes in thyroid function (at the start of treatment, periodically during treatment, and as indicated based on clinical evaluation) and for clinical signs and symptoms of thyroid disorders.

- **Grade 2** hyperthyroidism events (and **Grade 2-4** hypothyroidism):
  - In hyperthyroidism, non-selective beta-blockers (e.g. propranolol) are suggested as initial therapy.
  - In hypothyroidism, thyroid hormone replacement therapy, with levothyroxine or liothyronine, is indicated per standard of care.
- **Grade 3-4** hyperthyroidism
  - Treat with an initial dose of IV corticosteroid followed by oral corticosteroids. When symptoms improve to Grade 1 or less, steroid taper should be started and continued over no less than 4 weeks. Replacement of appropriate hormones may be required as the steroid dose is tapered.

• **Hepatic:**

- For **Grade 2** events, monitor liver function tests more frequently until returned to baseline values (consider weekly).
  - Treat with IV or oral corticosteroids
- For **Grade 3-4** events, treat with intravenous corticosteroids for 24 to 48 hours.
- When symptoms improve to Grade 1 or less, a steroid taper should be started and continued over no less than 4 weeks.

• **Renal Failure or Nephritis:**

- For **Grade 2** events, treat with corticosteroids.
- For **Grade 3-4** events, treat with systemic corticosteroids.
- When symptoms improve to Grade 1 or less, steroid taper should be started and continued over no less than 4 weeks.

- **Management of Infusion Reactions:** Signs and symptoms usually develop during or shortly after drug infusion and generally resolve completely within 24 hours of completion of infusion.

**Table 5** below shows treatment guidelines for subjects who experience an infusion reaction associated with administration of pembrolizumab (MK-3475).

Table 5 Infusion Reaction Treatment Guidelines

NCI CTCAE Grade	Treatment	Premedication at subsequent dosing
Grade 1 Mild reaction; infusion interruption not indicated; intervention not indicated	Increase monitoring of vital signs as medically indicated until the subject is deemed medically stable in the opinion of the investigator.	None
Grade 2 Requires infusion interruption but responds promptly to symptomatic treatment (e.g., antihistamines, NSAIDS, narcotics, IV fluids); prophylactic medications indicated for <=24 hrs	
Stop Infusion and monitor symptoms.                      Additional appropriate medical therapy may include but is not limited to:
 
 
IV fluids
 
Antihistamines
 
NSAIDS
 
Acetaminophen
 
Narcotics
 
 
Increase monitoring of vital signs as medically indicated until the subject is deemed medically stable in the opinion of the investigator.                      If symptoms resolve within one hour of stopping drug infusion, the infusion may be restarted at 50% of the original infusion rate (e.g., from 100 mL/hr to 50 mL/hr). Otherwise dosing will be held until symptoms resolve and the subject should be premedicated for the next scheduled dose.
 
Subjects who develop Grade 2 toxicity despite adequate premedication should be permanently discontinued from further trial treatment administration.
	Subject may be premedicated 1.5h ( $\pm$ 30 minutes) prior to infusion of pembrolizumab (MK-3475) with: Diphenhydramine 50 mg po (or equivalent dose of antihistamine). Acetaminophen 500-1000 mg po (or equivalent dose of antipyretic).
Grades 3 or 4  Grade 3: Prolonged (i.e., not rapidly responsive to symptomatic medication and/or brief interruption of infusion); recurrence of symptoms following initial improvement; hospitalization indicated for other clinical sequelae (e.g., renal impairment, pulmonary infiltrates)  Grade 4: Life-threatening; pressor or ventilatory support indicated	
Stop Infusion.                      Additional appropriate medical therapy may include but is not limited to:
 
 
IV fluids
 
Antihistamines
 
NSAIDS
 
Acetaminophen
 
Narcotics
 
Oxygen
 
Pressors
 
Corticosteroids
 
Epinephrine
 
 
Increase monitoring of vital signs as medically indicated until the subject is deemed medically stable in the opinion of the investigator.                      Hospitalization may be indicated.
 
Subject is permanently discontinued from further trial treatment administration.
	No subsequent dosing
Appropriate resuscitation equipment should be available in the room and a physician readily available during the period of drug administration.		

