## SUMMARY OF CHANGES

### PRIMARY REASON(S) FOR THIS AMENDMENT:

Section Number (s)	Section Title(s)	Description of Change (s)	Rationale
Change from Amendment 055-04 to 055-05			
2.2	Trial Diagram	The trial diagram adding pembrolizumab extension trial after survival follow-up was replaced with the correct trial diagram.	Correction.
Changes from Amendment 055-03 to 055-05			
6.1	Initial Treatment Phase and Second Course Phase (Retreatment)	Survival status activities are shown taking place throughout the trial.  The frequency of telephone contacts during the survival follow-up phase was changed from every 12 weeks to approximately every 12 weeks.	This change enables flexibility of survival status activities, to ensure that current, complete survival data are available at the time of database locks.  To enable flexibility of survival status activities
7.1.5.3.3	Survival Follow-Up	The frequency of telephone contacts during the survival follow-up phase was changed from every 12 weeks to approximately 12 weeks.	To enable flexibility of survival status activities.
7.1.5.4	Survival Status	This section was added to state that the Sponsor may request updated survival data during the course of the study.	To ensure that current and complete survival data are available at the time of database locks

Section Number (s)	Section Title(s)	Description of Change (s)	Rationale
5.2.1.2	Dose Modification (Escalation/Titration/Other)	The dose modification guidelines were replaced; the replacement guidelines identify specific immune-related adverse events associated with pembrolizumab.	To provide current comprehensive guidelines for management of immune related adverse events.

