4.2.2.1	Efficacy Endpoints	Reference 32 is renumbered 31.	Sequence of references

Section Number (s)	Section Title (s)	Description of Change (s)	Rationale
8.2.7	Sample Size and Power Calculations	Reference 29 is renumbered 28.	Sequence of references
11.0	List of References	References 29, 28, and 32 are renumbered 28, 29, and 31.	Sequence of references
		Reference 30 is corrected.	Incorrect reference in previous protocol versions
		References 31, 33 to 41, and 43 to 49 in previous protocol versions are removed.	These references are not cited in the text.
12.4	Abbreviations	eCRF (electronic Case Report Form) is added. ORST (Oncologic Response-Solid Tumor) is defined.	This abbreviation had not been in Section 12.4. This abbreviation had not been defined in the text.

No additional changes.

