#### **5.2.1.2 Dose Modification (Escalation/Titration/Other)**

Adverse events (both non-serious and serious) associated with pembrolizumab exposure may represent an immunologic etiology. These adverse events may occur shortly after the first dose or several months after the last dose of treatment. Pembrolizumab must be withheld for drug-related toxicities and severe or life-threatening AEs as per [Table 3](#) below. See Section 5.6 and the Events of Clinical Interest Guidance Document for supportive care guidelines, including use of corticosteroids.

Table 3 Dose Modification and Toxicity Management Guidelines for Immune-related AEs Associated with Pembrolizumab

General instructions:				
Immune-related AEs	Toxicity grade or conditions (CTCAEv4.0)	Action taken to pembrolizumab	irAE management with corticosteroid and/or other therapies	Monitor and follow-up
Pneumonitis	Grade 2	Withhold	
 
Administer corticosteroids (initial dose of 1-2 mg/kg prednisone or equivalent) followed by taper
 
	
 
Monitor subjects for signs and symptoms of pneumonitis
 
Evaluate subjects with suspected pneumonitis with radiographic imaging and initiate corticosteroid treatment
 
Add prophylactic antibiotics for opportunistic infections
 

	Grade 3 or 4, or recurrent Grade 2	Permanently discontinue		
Diarrhea / Colitis	Grade 2 or 3	Withhold	
 
Administer corticosteroids (initial dose of 1-2 mg/kg prednisone or equivalent) followed by taper
 
	
 
Monitor subjects for signs and symptoms of enterocolitis (ie, diarrhea, abdominal pain, blood or mucus in stool with or without fever) and of bowel perforation (ie, peritoneal signs and ileus).
 
Subjects with <math>\geq</math> Grade 2 diarrhea suspecting colitis should consider GI consultation and performing endoscopy to rule out colitis.
 
Subjects with diarrhea/colitis should be advised to drink liberal quantities of clear fluids. If sufficient oral fluid intake is not feasible, fluid and electrolytes should be substituted via IV infusion.
 

	Grade 4	Permanently discontinue		

Immune-related AEs	Toxicity grade or conditions (CTCAEv4.0)	Action taken to pembrolizumab	irAE management with corticosteroid and/or other therapies	Monitor and follow-up

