Immune-related AEs	Toxicity grade or conditions (CTCAEv4.0)	Action taken to pembrolizumab	irAE management with corticosteroid and/or other therapies	Monitor and follow-up
Myocarditis	Grade 1 or 2	Withhold	
 
Based on severity of AE administer corticosteroids
 
	
 
Ensure adequate evaluation to confirm etiology and/or exclude other causes
 

	Grade 3 or 4	Permanently discontinue		
All other immune-related AEs	Intolerable/ persistent Grade 2	Withhold	
 
Based on type and severity of AE administer corticosteroids
 
	
 
Ensure adequate evaluation to confirm etiology and/or exclude other causes
 

	Grade 3	Withhold or discontinue based on the type of event. Events that require discontinuation include and not limited to: Guillain-Barre Syndrome, encephalitis		
	Grade 4 or recurrent Grade 3	Permanently discontinue		

1. Withhold or permanently discontinue pembrolizumab is at the discretion of the investigator or treating physician.
 
NOTE:  For subjects with Grade 3 or 4 immune-related endocrinopathy where withhold of pembrolizumab is required, pembrolizumab may be resumed when AE resolves to <math>\leq</math> Grade 2 and is controlled with hormonal replacement therapy or achieved metabolic control (in case of T1DM).
				

In case toxicity does not resolve to Grade 0-1 within 12 weeks after last infusion, trial treatment should be discontinued after consultation with the Sponsor. Subjects who experience a recurrence of the same severe or life-threatening event at the same grade or greater with rechallenge of pembrolizumab (MK-3475) should be discontinued from trial treatment. With Investigator and Sponsor agreement, subjects with a laboratory adverse event still at Grade 2 after 12 weeks may continue treatment in the trial only if asymptomatic and controlled. For information on the management of adverse events, see Section 5.6.1.

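### Table 3 lists steroids for Grade 2 or 3 diarrhea/colitis with no wait, while Section 5.6 ties them to more than 3 days (Grade 2) or more than 1 week (Grade 3 or 4), and no readable text says which governs

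*Combined protocol and SAP*

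**What the plan says.** Section 5.2.1.2, Table 3, has one diarrhea/colitis row for Grade 2 or 3. The drug action is to withhold pembrolizumab. The corticosteroid column reads "Administer corticosteroids (initial dose of 1-2 mg/kg prednisone or equivalent) followed by taper". No duration or persistence is required before steroids begin. Grade 4 calls for permanent discontinuation; its steroid cell is blank in the text available to us.

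The paragraph before Table 3 refers sites onward: "See Section 5.6 and the Events of Clinical Interest Guidance Document for supportive care guidelines, including use of corticosteroids".

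Section 5.6 then makes steroids for the same disorder conditional on how long it lasts. For Grade 2 the instruction applies to an event "that persists greater than 3 days, administer oral corticosteroids". For Grade 3 or 4 it applies to an event "that persists > 1 week, treat with intravenous steroids followed by high dose oral steroids".

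Section 5.6 describes its content as suggested measures, to be applied once the investigator judges the event related to pembrolizumab. It points back to Section 5.2.1 for dose modification only.

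**The concern.** Two parts of the same protocol give different conditions for starting steroids at Grades 2 and 3. The conditions in Section 5.6 also run against severity: the more dangerous event has the longer wait.

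A site working from Table 3 could treat a Grade 3 event at once. A site working from the Section 5.6 bullets could wait more than a week for the same event, or for a Grade 4 one. Both texts tell sites to watch for bowel perforation in this disorder. What is at stake is delayed or inconsistent treatment of a potentially serious toxicity, in a trial whose first primary objective is safety and tolerability.

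**Working it through.** No sample size, power or error rate is involved. The check compares the texts, looks at how the rest of Section 5.6 is written, and follows the cross-references.

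**1. Triggers side by side (diarrhea/colitis)**

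| Grade | Table 3 | Section 5.6 |
|---|---|---|
| 2 | Steroids, no wait stated | Oral steroids after more than 3 days |
| 3 | Steroids, no wait stated | IV, then high-dose oral, after more than 1 week |
| 4 | Steroid cell blank in the available text | IV, then high-dose oral, after more than 1 week |

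The readable texts differ at Grades 2 and 3. Within Section 5.6 the Grade 3 or 4 threshold exceeds the Grade 2 threshold by 7 − 3 = 4 days.

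**2. Is a wait usual in Section 5.6?** Grade-specific steroid instructions, leaving out the infusion-reaction table:

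- pneumonitis: 2 (Grade 2; Grade 3-4)
- diarrhea/colitis: 2 (Grade 2; Grade 3 or 4)
- hypophysitis: 2 (Grade 2; Grade 3-4)
- hyperthyroidism: 1 (Grade 3-4)
- hepatic: 2 (Grade 2; Grade 3-4)
- renal: 2 (Grade 2; Grade 3-4)

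Total: 2 + 2 + 2 + 1 + 2 + 2 = 11 instructions across 6 disorders. A persistence condition appears in 2 of 11, both for diarrhea/colitis, so in 1 of 6 disorders. By contrast, Grade 3-4 pneumonitis is to be treated immediately, and for Grade 3-4 hypophysitis the text is simply "treat with an initial dose of IV corticosteroids followed by oral corticosteroids".

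**3. Does Table 3 state persistence where it is meant?** Yes. The row for all other immune-related events uses "Intolerable/ persistent Grade 2" as a condition for withholding drug. The diarrhea/colitis row has no such wording.

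**4. Is the wait consistent with the protocol's own grading?** Table 8 describes Grade 3 as severe, with hospitalization indicated, and Grade 4 as life-threatening and needing urgent intervention. A wait of more than a week does not fit either description.

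**5. Does a cross-reference settle precedence?** Section 5.2.1.2 points to Section 5.6 and to an external document without ranking them. Section 5.6 points back for dose modification only. The text after Table 3 points to a Section 5.6.1, and Section 7.1.2.1 to a Section 5.6.1.1; neither is in the table of contents or the body. No readable text ranks one instruction above the other.

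**The case against.** The strongest reply is that the two texts do different jobs: Table 3 gives the drug action and starting dose, and Section 5.6, to which sites are expressly referred, adds timing, route and taper. Silence in Table 3 is then not a contradiction. This is a fair reading, but it makes the wait of more than a week the operative rule for Grade 3 or 4 events, so the wording would still need correction.

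A persistence condition could also reflect diagnostic work-up, since diarrhea is non-specific and Section 5.6 asks for infection to be ruled out and endoscopy to be considered. That has some force for Grade 2. It does not explain the Grade 3 or 4 wait, because the guidance applies once the event has been judged drug-related.

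Several points on the other side do stand:

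- Section 5.6 is suggested care under the investigator's judgement, and Section 5.5.2 allows steroids for suspected immune-related events of clinical interest.
- Withholding and discontinuation under Table 3 are unaffected.
- The general-instructions row and the Grade 4 steroid cell of Table 3 are blank in the available text, perhaps through extraction, and the events-of-clinical-interest guidance document was not supplied. A governing rule could sit in any of these.
- The change log states "The dose modification guidelines were replaced; the replacement guidelines identify specific immune-related adverse events associated with pembrolizumab" for Section 5.2.1.2 and does not list Section 5.6, which suggests that Section 5.6 is the older text. This is weak evidence, and the conclusion does not depend on it.

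**Conclusion.** The concern holds. The steroid triggers differ at Grades 2 and 3, the Section 5.6 waits are inverted by 4 days relative to severity, and no readable text resolves the difference. A precedence rule elsewhere would settle which text governs, but the one-week condition would remain printed in the protocol.

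The number of subjects affected cannot be estimated, because the documents give no rate for Grade 2 or higher immune-related colitis. No endpoint or statistical figure changes. The change should be made because it bears on subject safety and is cheap; investigator discretion keeps it from being more serious. Confidence is medium, given the blank Table 3 cells and the guidance document that could not be seen.

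**What to change.** In the Grade 3 or 4 diarrhea/colitis bullet of Section 5.6, delete the condition that the event must last more than 1 week. Table 3 supports this for Grade 3, and the Table 8 description of Grade 4 supports it for Grade 4.

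For Grade 2 the timing is a clinical choice for the sponsor. Either state that Table 3 governs when steroids start, or put the same more-than-3-day condition in both Table 3 and Section 5.6.

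Check that the events-of-clinical-interest guidance document agrees, and notify sites. The cost is an edit to one or two bullets, possibly one Table 3 cell, and a site communication. There is no statistical cost.
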